## **Progression Criteria for a Full Trial**

We will progress for a full trial if we achieve our target recruitment and acquire post-intervention (25 weeks) ITQ data from  $\geq 75\%$  of those randomised.

## **STATISTICAL CONSIDERATIONS**

### **Sample size**

There are currently no effectiveness studies on the psychological interventions for CPTSD to enable power calculations. Following a pragmatic approach and in line with previous pilot studies in the area of PTSD we will aim to recruit  $n=30$  individuals per arm (total sample = 60). This approach will enable us calculating sample size for an adequately powered trial.

### **Data analysis**

#### ***Recruitment and Retention***

Recruitment and retention rates at all stages of the trial will be recorded and summarised as counts and percentages.

#### ***Quantitative analyses***

The main analyses of the trial data will be conducted in 2 phases; (1) modelling within-subject changes in ITQ scores for data from the ESTAIR arm of the trial and a (2) comparison between the ITQ scores, and secondary outcome measures, for the ESTAIR and TAU groups at 25 weeks and 12 week follow-up.

Phase 1: An analogue to a repeated measures ANOVA will be specified as a structural equation model to handle missing data efficiently using robust maximum likelihood estimation (MLR: Schafer & Graham, 2002) and relax assumptions about the variance-covariance structure of the observations (Hoffman, 2015). An initial model will specify and estimate a model with the mean ITQ scores from the five observation periods (baseline, 7, 13, 19, 25 months) constrained to be equal, and then the model will be re-estimated with the means to be freely estimated. The difference in model fit can be tested using the loglikelihood difference test, which is distributed as a chi-square ( $\chi^2$ ). A significant  $\chi^2$  result indicates that the unconstrained model is better than the constrained model, meaning that the null hypothesis of equal means can be rejected (Hoffman, 2015). If this is the case pairwise differences in means will be tested using the Wald  $\chi^2$  test. The magnitude of the change in symptoms scores will be calculated using Cohen's  $d$  with a correction for repeated measures designs (dr). Values  $< 0.40$  reflect 'small' effects, values from 0.40 to 0.79 reflect 'medium' effects, and values  $> 0.80$  reflect 'large' effects.

Phase 2: The primary intention to treat analysis will be conducted to examine differences between the ESTAIR and TAU groups at 25 weeks. This analysis will be conducted using a regression approach, simultaneously regressing the 25 week mean scores of the ITQ, PHQ-9, GAD-7, PHQ-15, and AUDIT onto a dummy-coded binary variable representing the treatment and control group (ESTAIR = 1, TAU = 0). The estimated regression coefficient for each variable indicates the mean difference between the treatment and control group, and the associated  $p$ -values indicate statistical significance. This approach was used as (1) all the model parameters are estimated simultaneously thereby avoiding the need for post-hoc adjustment for multiple testing, (2) the use of robust maximum likelihood (MLR) estimation allows for missing data to be handled efficiently by using all available data (Schafer & Graham, 2002), and third, MLR estimation is robust against deviations from normality and produces unbiased standard errors (West, Finch, & Curran, 1995). Furthermore, the

standardised regression coefficients from this model can be used as a useful analogue to Cohen's *d* as a measure of effect size (Nieminen, Lehtiniemi, Vähäkangas, Huusko, & Rautio, 2013): *d*=0.20 is a 'small' effect, *d*=0.50 is a 'medium' effect, and *d*=0.80 is 'large' effect size.

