## OUTCOME MEASURES

Outcomes are as follows: **(i)** Retention & data completion rates at weeks 25 weeks post-treatment and 12-week follow-up, on the primary outcome; International Trauma Questionnaire (Cloitre et al., 2018) and secondary outcomes: PHQ Depression (Kroenke et al., 2001), GAD Generalised Anxiety (Spitzer et al., 2006), AUDIT Substance Misuse (Saunders et al., 1993), and PHQ-15 Medically Unexplained Symptoms (Kroenke et al., 2002) **(ii)** 12-month recruitment rate; **(iii)** participant & clinical staff views on trial & intervention acceptability and suggested changes. Baseline information on demographics including age, gender, marital status etc., will be gathered to characterise the sample.

A range of assessments will be administered by the research assistant to test the acceptability of primary (PTSD and CPTSD) (i.e. ITQ) and secondary outcomes (depression, anxiety, alcohol use, and somatisation) (e.g. GHQ-12, AUDIT). Participants in both groups will be asked to complete these outcome measures at baseline, after 25-weeks post-treatment and then again after at a 12-week follow-up. The ITQ will be also completed by the ESTAIR group at the end of every module. In addition, data will be recorded on retention and DNA rate. The research assistant will be masked to group allocation to demonstrate to future funders this is achievable in a future trial.

**Note:** The ITQ will be completed by the therapist and participant at the end of every model. Due to feasibility concerns, the research assistant will not be masked to group allocation when collected measures at baseline, post-treatment, and follow-up. This is not expected to have any impact on outcomes as all primary and secondary outcome measures are self-report.

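### Phase 1 lists an uncontrolled before-after test in the ESTAIR arm as a main analysis without saying that it cannot show benefit over TAU, and the randomised ITQ comparison leaves out baseline

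*Combined protocol and SAP*

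**What the plan says.** The Quantitative analyses section of the combined protocol and SAP opens: "The main analyses of the trial data will be conducted in 2 phases". Phase 1 is "modelling within-subject changes in ITQ scores for data from the ESTAIR arm of the trial". It fits one model with the five ITQ means held equal and one with them free, and compares the fits by a chi-square test. A significant result is read as "meaning that the null hypothesis of equal means can be rejected". Pairwise Wald tests follow, and the size of the change is graded on bands, for example "values from 0.40 to 0.79 reflect 'medium' effects". The section does not call this descriptive or exploratory, and sets no limit on what may be concluded from it.

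Phase 2 is the randomised comparison: "The primary intention to treat analysis will be conducted to examine differences between the ESTAIR and TAU groups at 25 weeks". It is done by "simultaneously regressing the 25 week mean scores of the ITQ, PHQ-9, GAD-7, PHQ-15, and AUDIT onto a dummy-coded binary variable" for arm. No baseline term is described. The opening of the section also promises a comparison at the 12-week follow-up, but Phase 2 sets out a model for 25 weeks only.

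On data collection, the Outcome Measures section says "Participants in both groups will be asked to complete these outcome measures at baseline, after 25-weeks post-treatment", and again at the 12-week follow-up. The module-end assessments are confined to one arm: "The ITQ will be also completed by the ESTAIR group at the end of every module".

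**The concern.** Rejecting equal means in the ESTAIR arm shows that scores moved. It cannot separate an effect of ESTAIR from natural recovery, contact with the service, repeated completion of the questionnaire, or regression to the mean after entry on an ITQ-based criterion. TAU participants are exposed to the same influences, and their ITQ is collected at baseline, 25 weeks and follow-up. Yet no model in the plan uses TAU's change from baseline: Phase 1 leaves TAU out, and Phase 2 leaves baseline out.

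What is at stake is interpretation. A significant chi-square and a medium or large label, reported as a main analysis beside a between-arm comparison of 30 per arm, invite the reader to take within-arm change as evidence of benefit. The two sets of labels also differ: medium begins at 0.40 in Phase 1 and is set at 0.50 in Phase 2, so a within-arm change of 0.45 would be called medium while a between-arm difference of 0.45 would fall short of that benchmark. The Sample size section says the pilot will allow a full trial to be sized, and the plan does not say which estimate will be used for that.

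**Working it through.** **The plan's own figure.** The only relevant one is the sample size: 30 + 30 = 60. It was set pragmatically, with no effect size, SD, power or alpha, so there is no calculation to reproduce.

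**Inputs from the plan.**
- 30 participants per arm (Sample size).
- Five occasions in Phase 1. The last is taken as the 25-week assessment, although Phase 1 gives its times in months.
- At least 75% of those randomised with 25-week ITQ data (Progression Criteria): 0.75 × 30 = 22.5, taken as 23.

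**Assumptions, not in the plan.** Two-sided alpha 0.05; SD 1 at each occasion; equal correlation r of 0.5 to 0.7 between occasions; the same linear fall of d SD in both arms, with d = 0.3 or 0.5; complete data on the n participants. The true ESTAIR versus TAU difference is zero.

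**Step 1: chance that the Phase 1 null is rejected.** The exact small-sample test of five equal means (Hotelling T-squared) is used first, so that chi-square approximation error is kept out. Under linear drift the means are 0, d/4, d/2, 3d/4 and d, and their sum of squares about the average is d² × (1/4 + 1/16 + 0 + 1/16 + 1/4) = 0.625 d². The noncentrality is

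λ = n × 0.625 d² / (1 − r),

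and the test refers to F with 4 and n − 4 degrees of freedom. For n = 30, d = 0.3 and r = 0.5: λ = 30 × 0.625 × 0.09 / 0.5 = 3.375, the critical value of F(4, 26) is 2.743, and the probability of rejection is 23.2%.

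| n | d | r = 0.5 | r = 0.7 |
|---|---|---|---|
| 30 | 0.3 | λ = 3.375: 23.2% | λ = 5.625: 37.5% |
| 30 | 0.5 | λ = 9.375: 59.5% | λ = 15.625: 83.8% |
| 23 | 0.3 | λ = 2.588: 17.5% | λ = 4.313: 27.4% |
| 23 | 0.5 | λ = 7.188: 44.5% | λ = 11.979: 68.4% |

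**Step 2: the planned chi-square version.** Simulation of the likelihood-ratio test on 4 degrees of freedom (20,000 replicates, normal complete data) gives higher rates.
- n = 30: 29.5% to 45.0% at d = 0.3, and 66.9% to 88.6% at d = 0.5.
- n = 23: 24.8% to 37.1% at d = 0.3, and 55.2% to 77.9% at d = 0.5.
- With no change at all it rejects in 7.5% to 8.6%. That is small-sample inflation, a separate matter.

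**Step 3: the between-arm comparison in the same simulated trials.** A two-sample test of 25-week scores, and one of change from baseline, each rejects in 4.6% to 5.2% in every scenario. Shared change does not disturb either.

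**Step 4: what the unused baseline is worth.** Adjusting the 25-week contrast for baseline multiplies its variance by about 1 − r². That is 1 − 0.25 = 0.75 at r = 0.5 and 1 − 0.49 = 0.51 at r = 0.7, so the variance is about 25% to 49% lower.

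**The case against.** The strongest reply is that the randomised comparison is present and named primary. By randomisation, comparing 25-week scores already controls for natural recovery, service contact and repeated testing, as Step 3 confirms. Adding baseline improves precision; it does not cure confounding. Nor does Phase 1 say that its result is a treatment effect: its stated null is equal means over time. An arm-only account is also partly forced by the design, because the three intermediate ITQ assessments have no TAU counterpart. Finally, no stated decision rests on Phase 1: the research questions concern recruitment, retention and acceptability, and progression depends on recruitment and 25-week ITQ completeness.

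All of this stands, and it rules out several stronger readings that a reader might infer.

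- That the trial lacks a controlled efficacy analysis. Phase 2 is one.
- That 23% to 84% is a false-positive rate to be set against 5%. If means really fall, rejecting equal means is correct. The figures are power against a true within-arm change and become errors only if the result is read as efficacy.
- That the Phase 1 effect must exceed the randomised one. In expected mean change, that holds only if TAU also improves. If TAU is flat the two coincide, and if TAU worsens the randomised contrast is larger. The Treatment as Usual section, whose update note describes less than the original text, does not settle which to expect.
- That a spurious Phase 1 signal would launch a full trial. The progression criteria do not use it.

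The objection does not explain why a description of change across modules needs a null test, effect labels and main-analysis standing, or why a baseline measured in both arms is left out of the randomised comparison.

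**Conclusion.** The point holds as one of standing, labelling and efficiency. The plan should change, but the primary comparison is not invalid. An ESTAIR-only before-after test is listed as a main analysis and graded in effect terms with no statement that it cannot show benefit over TAU. Under an equal improvement of 0.3 to 0.5 SD in both arms, it would be significant in about 23% to 84% of trials at n = 30 and 17% to 68% at n = 23, while carrying no information on ESTAIR versus TAU.

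The size of the drift, its linearity, the correlations and alpha are all assumptions, so the percentages are illustrative. The direction is not: any shared change raises the Phase 1 rejection rate and leaves the between-arm rate near 5%. The gain from baseline adjustment, about 25% to 49% lower variance, rests on the same assumed correlations.

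**What to change.** 1. Present Phase 1 as descriptive: ITQ means and changes by module in the ESTAIR arm, with confidence intervals. Drop the test of equal means, the pairwise tests and the small, medium and large labels, and state that within-arm change is not evidence of benefit over TAU.
2. Rest every effect statement on one between-arm ITQ model that uses the baseline value and the occasions both arms share (baseline, 25 weeks and the 12-week follow-up), with the 25-week contrast named as primary. The planned robust maximum likelihood estimation can be kept.
3. State that this model replaces the unadjusted ITQ regression in Phase 2. Run beside it, it would create two between-arm ITQ tests with no rule for which governs.

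The model also supplies the follow-up comparison that the section promises but does not specify. No new data are needed. The cost is the uncontrolled within-arm p-value and a rewording of the Phase 2 ITQ model.

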## STUDY INTERVENTIONS

### **Enhanced Skills Training in Affective and Interpersonal Regulation (ESTAIR) (Cloitre et al., 2019)**

ESTAIR will be offered according to the protocol (Cloitre et al., 2019) by an experienced psychotherapist appointed for the study and trained to its delivery. Treatment sessions will be conducted individually. ESTAIR will consist of up to 25 sessions organised in 4 modules of about 6 sessions each tackling the symptoms of PTSD and DSO symptoms. The first initial session is a formulation session to link present difficulties and traumatic life events, discuss current issues and concerns, and collaboratively agree on relevant treatment goals.

ESTAIR entails a flexible application of tools that match participants' specific needs. The PTSD module provides narrative exposure to the traumatic memories and targets re-experiencing, avoidance, and hyperarousal symptoms. The AD module focuses on identifying and labelling feelings, emotion management, distress tolerance, and acceptance of feelings and experiencing positive emotions. The NSC module focuses on how to stay in the present moment and combat dissociation; self-compassion and mindfulness skills; challenging thinking patterns and developing a balanced view of self. The DR module focuses on exploration and revision of maladaptive schemas; effective assertiveness; awareness of social context; and flexibility in interpersonal expectations and behaviours that are displayed in social interactions.

**Update Note:** During the training of the psychotherapist in the ESTAIR intervention, slight modifications to the treatment protocol were made.

1. Given the pilot nature of the present study, it was determined that the modules would be delivered in a sequential manner, starting with the AD module, the DR module, the NSC module, and then finishing with the PTSD module if necessary.
2. It was determined that the ESTAIR protocol still consists of up to 25 sessions, starting with the initial formulation session and ending with the final summary and

relapse-prevention session. However, the number of sessions per module were modified from up to 6 sessions per module, to up to 5, 6, 5 and 7 sessions for the AD, DR, NSC and PTSD modules, respectively.

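### Phase 1 uses large-sample chi-square tests and unadjusted pairwise comparisons in at most 30 people, so false claims of symptom change are likelier than a nominal 5% level implies

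*Combined protocol and SAP*

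**What the plan says.** The Quantitative analyses section splits the main analyses into two phases. Phase 1 models within-subject change in the ESTAIR arm only, as a structural equation model fitted by robust maximum likelihood (MLR) with relaxed covariance assumptions. A model with five equal means is compared with one in which the means are free: "The difference in model fit can be tested using the loglikelihood difference test, which is distributed as a chi-square". A significant result opens the next step: "If this is the case pairwise differences in means will be tested using the Wald" chi-square. No scaling, small-sample correction or adjustment for the number of pairs is mentioned. The five occasions are given as "baseline, 7, 13, 19, 25 months".

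Phase 2 regresses five outcomes on arm and states that "MLR estimation is robust against deviations from normality and produces unbiased standard errors".

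The Sample size section aims for 30 "individuals per arm (total sample = 60") and gives no power calculation. No significance level appears; Phase 2 says only that the p-"values indicate statistical significance".

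**The concern.** The chi-square law for a log-likelihood difference is a large-sample result. With five means, an unrestricted covariance matrix and at most 30 people, the statistic has a heavier upper tail than chi-square on 4 degrees of freedom, so the test rejects too often. Under MLR, moreover, the raw difference is not chi-square distributed even in large samples; it needs a scaling correction.

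The pairwise step adds a separate problem. Requiring a significant overall test protects against false pairwise claims only when all five means are equal. Once ITQ scores fall from baseline, as the investigators hope, the gate opens and every remaining true-null pair is tested at the full unadjusted level. At stake are statements that symptoms changed, and between which modules.

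**Working it through.** **Inputs.** n is at most 30 in the ESTAIR arm (Sample size). At the 75% ITQ completeness threshold (Progression Criteria), 0.75 × 30 = 22.5, so n is 22 to 23. Five means give 4 degrees of freedom and 5 × 4 / 2 = 10 pairs. Alpha is not stated; 0.05 is assumed throughout. The plan gives no error rate to reproduce.

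**Overall test.** For complete normal data, unstructured covariance and an unscaled difference, LRT = n·ln(1 + T²/(n−1)), where T² is Hotelling's statistic and T²/(n−1) = [4/(n−4)]·F with F distributed as F(4, n−4). The planned test rejects when LRT > 9.488, so its true size is P{F(4, n−4) > [(n−4)/4]·(exp(9.488/n) − 1)}.

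| n | exp(9.488/n) − 1 | F cut-off implied by the plan | Correct 5% F cut-off | True size |
|---|---|---|---|---|
| 30 | 0.372 | 6.5 × 0.372 = 2.418 | 2.743 | 7.4% |
| 23 | 0.511 | 4.75 × 0.511 = 2.425 | 2.895 | 8.4% |
| 22 | 0.539 | 4.5 × 0.539 = 2.426 | 2.928 | 8.6% |

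A simulation of full-information maximum likelihood with 25% monotone dropout from n=30 (1,500 trials) gave about 8.6%.

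**Each pairwise test.** The Wald statistic with maximum likelihood variance rejects when |t| on n−1 degrees of freedom exceeds 1.96·√((n−1)/n). At n=30 the cut-off is 1.927 and the size 6.4%; at n=22 they are 1.915 and 6.9%.

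**At least one false pairwise claim, gate applied.** Simulated with normal data and common correlation 0.5, 20,000 trials per case:

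| True pattern of means | As planned, n=30 | As planned, n=22 to 23 | Exact F and t, no adjustment |
|---|---|---|---|
| All five equal | about 7% | 8% to 9% | about 5% |
| Steady decline, last two equal | 6% to 7% | about 7% | about 5% |
| Baseline 1 SD higher, four later means equal (6 null pairs) | 25% | 27% | 20% to 21% |

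In the last row, correcting the reference distribution removes only about 4 to 6 points; the rest is unadjusted multiplicity. With t references and Holm adjustment over the ten pairs, the error in that row falls to about 4%.

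**Phase 2.** With maximum likelihood variance and a z reference, each test rejects when |t| on 2n−2 degrees of freedom exceeds 1.96·√((2n−2)/(2n)), where n is now per arm. The size is 5.9% at 30 per arm and 6.2% at 22 to 23 per arm.

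**Occasions.** The labels 7, 13, 19 and 25 equal 1 + 6k for k = 1 to 4: one formulation session plus four six-session modules. They read as sessions or weeks, not months. Outcome measures, Procedure and the progression rule all place post-treatment at 25 weeks. Study design gives a 28-month study and Outcome measures a 12-month recruitment rate; someone enrolled at month 12 would reach 25 months at month 12 + 25 = 37. The ESTAIR update note also changed the modules to "up to 5, 6, 5 and 7 sessions for the AD, DR, NSC and PTSD modules, respectively", so the latest module ends are sessions 1+5 = 6, 6+6 = 12, 12+5 = 17 and 17+7 = 24.

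**The case against.** The strongest reply is that little hangs on this. The four research questions concern recruitment, retention and acceptability. Progression depends on recruitment and ITQ completeness, not on a p-value. Phase 1 has no control group, and Sample size concedes that "There are currently no effectiveness studies on the psychological interventions for CPTSD to enable power calculations". All of this stands, and it limits the consequence.

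Several stronger readings are tempting but unsupported:

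- A reader might infer that the plan promises 5% and breaks the promise. It states no alpha; every percentage here rests on an assumed 0.05.
- A reader might take about 26% as the general pairwise error rate. The gate holds it to about 7% to 9% when nothing changes, and it is 6% to 7% under a steady decline. The higher figure needs an early drop followed by four equal means.
- A reader might blame that figure on the chi-square reference. Exact tests still give 20% to 21%, so missing adjustment is the main cause.
- A reader might extend the point to Phase 2 or to confidence intervals. The Phase 2 z reference is implied rather than written, its inflation is small, and neither phase specifies a confidence interval.

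The plan also does not say that the difference will be left unscaled; it is silent. The scaled MLR statistic was not simulated, so its size here is unknown. The month labels are a separate consistency error with no bearing on error rates.

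**Conclusion.** The point holds for Phase 1. The chi-square reference is too liberal at this sample size: 7.4% at n=30 and about 8.5% at n=22 to 23 against an assumed 5%, with pairwise tests at 6.4% to 6.9% each. The overall-test figures are exact for complete normal data and an unscaled difference, and approximate for the MLR analysis with missing data that the plan intends. The larger exposure, about 25% to 27%, is conditional on a baseline difference with equal later means and comes mostly from the absent multiplicity adjustment. That pattern is plausible if most benefit arrives in the first module, and it is where claims about later modules would mislead. The Phase 2 wording is a minor matter at about 6% per test. No progression decision is affected. The correction is worth making because it is cheap and protects the claims about where change occurred.

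**What to change.** 1. State alpha and sidedness for both phases.
2. Test the Phase 1 overall hypothesis with a small-sample reference: for example, an unstructured mixed model with Kenward-Roger degrees of freedom, which keeps incomplete cases, or a Hotelling-type F(4, n−4) test, which is exact for complete normal data. If the MLR likelihood difference is retained, say that the scaled difference will be used and that its small-sample size has been checked.
3. Use t references with Holm adjustment for the ten pairwise tests. Changing the reference alone would not be enough.
4. In Phase 2, describe the claim about standard errors as a large-sample property.
5. Separately, replace the month labels with baseline and the end of each module, and say whether the fifth occasion is the end of the PTSD module or the 25-week assessment. These may fall at different times, and the plan collects the ITQ at both.

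The cost is a few sentences of analysis plan and a few lines of code. P-values become slightly larger, and Holm gives up some power for individual module contrasts. No data collection changes.

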## **STUDY POPULATION AND RECRUITMENT**

Combat Stress received approximately 3400 veteran referrals across the UK between April 2018/2019. Based on a recently completed cohort study, it is predicted that about 1,900 will meet criteria for CPTSD. As such, potential participants will be recruited and screened via Combat Stress.

Potential participants will be drawn from those referred to the Southern Treatment Combat Stress Treatment Centre (Leatherhead). They will have completed a mental health assessment as part of the referral and registered with Combat Stress for treatment. Potential participants will meet criteria for CPTSD, as indicated by the ITQ completed during their initial assessment. All new referrals are discussed at a weekly case management meeting to determine eligibility based on the inclusion and exclusion criteria below:

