### **Inclusion criteria**

- Adults (18 years or older) in the caseload of Combat Stress
- UK armed forces veteran
- Help-seeking for trauma related psychological distress
- Meets diagnostic criteria for CPTSD as measured by the ITQ
- Proficiency in English language
- Signed informed consent provided

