### **Recruitment**

When entering Combat Stress' clinical service, veterans are offered a formal assessment by a member of the multi-disciplinary team (MDT). As part of this process, they complete various psychometric measures of health including the International Trauma Questionnaire (ITQ). All cases are discussed at a weekly case management meeting. The research assistant will be embedded within the clinical team at Combat Stress' treatment centre in Leatherhead, Surrey to facilitate recruitment for this study. Veterans meeting criteria for CPTSD on the ITQ and deemed ready for therapy by the MDT will be approached to participate in the study.

The following procedure will be followed to recruit participants for the study:

1. The research assistant will attend the case management meeting to screen veterans for eligibility for the study.
2. If eligible, the research assistant will approach potential participants by letter and will be sent the patient information sheet and consent form. This invitation will be followed up by telephone call by the research assistant to discuss questions about the study and to discuss participants' willingness to participate. At this meeting, it will be emphasised that participation is voluntary.

**Note:** Due to the COVID-19 pandemic, the patient information sheet and consent form letter will be sent to potential participants via email, and they will later receive a printed copy by post.

3. If willing to participate, participants will be asked to attend a one to one or on-line meeting with the research assistant. At this meeting they will be asked again if they have any questions about the study, sign the consent form and complete pre-treatment measures. All forms can also be returned via mail. Following this, they will be randomised to one of the two groups (TAU or ESTAIR).
4. The research assistant will then inform Combat Stress of the outcome so participants in the TAU or who opted out can be offered the standard treatment.

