## **PROCEDURE**

Potential participants will be screened by the MDT team, and eligible participants will be contacted by the research assistant. As previously described in the **Recruitment** section above, eligible participants will be provided with the patient information sheet and consent form. Potential participants will be contacted by the research assistant, who will ensure that they have received an information sheet and will answer any questions. All potential participants will be reminded that participation is entirely voluntary and that deciding not to

take part in the study will have no impact upon the clinical care they receive. They will also be informed of their right to withdraw from the study at any time, without giving a reason, and reassured that exercising their right to withdraw will have no impact upon the ongoing care they receive. Potential participants who wish to take part will need to provide informed consent. Participants who are not eligible or who do not want to participate will be offered routine care as per Combat Stress procedures.

Eligible participants who provide consent to take part will complete baseline measures and will then be randomized to either the ESTAIR or TAU intervention arm. At 25-weeks (post-treatment), participants will be contacted by the research assistant to complete post-intervention measures. Participants in the ESTAIR arm will also be asked to provide qualitative data of their experience of intervention. The research assistant will then set an appointment to again contact participants in 12-weeks' time to complete the follow-up measures.

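### Free improvement: the primary between-arm model leaves out baseline scores already collected in both arms; adding each outcome's own baseline would narrow its interval

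*Combined protocol and SAP*

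**What the plan says.** Under Quantitative analyses, Phase 2, the plan states: "The primary intention to treat analysis will be conducted to examine differences between the ESTAIR and TAU groups at 25 weeks". The 25-week ITQ, PHQ-9, GAD-7, PHQ-15 and AUDIT scores are regressed together "onto a dummy-coded binary variable representing the treatment and control group". Each coefficient is read as the plain difference in arm means, with a p-value and effect-size benchmarks. No covariate is named there or anywhere else in the Data analysis section. The opening of the same section also announces a comparison at the 12-week follow-up.

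Baseline scores enter only Phase 1, described as "modelling within-subject changes in ITQ scores for data from the ESTAIR arm of the trial".

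The baseline data exist for both arms and precede allocation:

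- OUTCOME MEASURES: "Participants in both groups will be asked to complete these outcome measures at baseline".
- Recruitment, step 3: participants "sign the consent form and complete pre-treatment measures" and are randomised afterwards.
- PROCEDURE: "Eligible participants who provide consent to take part will complete baseline measures and will then be randomized".

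The Randomisation section describes permuted blocks and no stratification by severity. So neither the design nor the analysis uses baseline scores to compare the arms.

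**The concern.** A score measured before randomisation cannot be affected by treatment. If it predicts the 25-week score, adjusting for it removes variance that the arm-only comparison leaves in the error term. The plan collects these scores from everyone and then leaves them out of the analysis it labels primary. With about 45 participants analysed, the interval is already wide, and it is wider than the collected data require.

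The stake is precision only. The arm-only difference is valid under randomisation. Participants with no 25-week data contribute nothing to either model. Bias from dropout that differs by arm is possible, but the documents do not establish it and it is not part of this point.

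**Working it through.** There is no power figure to reproduce: the Sample size section sets 30 per arm pragmatically, without alpha, power, effect or SD.

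**Inputs**

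- Randomised: 60 (Sample size).
- Analysed: 45, from 0.75 × 60 (Progression Criteria), taken as 22 + 23.
- Two-sided 95% interval: assumed, since the plan states no level.
- r, the within-arm correlation of baseline with 25-week score: not in the documents; assumed 0.3, 0.5 and 0.7.

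**Net standard-error ratio, adjusted to arm-only**

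Ratio = √(1 − r²) × √((N − 3)/(N − 4)). The second factor is the cost of estimating the slope. At N = 45 it is √(42/41) = 1.0121.

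- Arm-only half-width: t(43) × √(1/22 + 1/23) = 0.601 SD.
- Adjusted half-width: 0.601 × ratio.
- Number of participants the arm-only model would need for the same precision: 45/ratio².

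| r | SE ratio | Simulated ratio | Half-width (SD) | Equivalent analysed N |
|---|---|---|---|---|
| 0.3 | 0.966 | 0.966 | 0.581 | 48.3 |
| 0.5 | 0.877 | 0.880 | 0.527 | 58.6 |
| 0.7 | 0.723 | 0.719 | 0.435 | 86.1 |

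The simulation used 40,000 trials at 22 + 23.

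**Break-even.** The ratio equals 1 when r² = 1/42, that is r = 0.154. At r = 0 the ratio is 1.012 (simulated 1.013), a loss of about 1%.

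**Range restriction for the ITQ.** The inclusion criteria require that a participant "Meets diagnostic criteria for CPTSD as measured by the ITQ". If this shrinks the baseline SD to a fraction u of its unselected value, then r′ = r·u/√(1 − r² + r²u²). With u assumed to be 0.6 or 0.8:

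| Unselected r | r′ (u = 0.6 / 0.8) | Net SE reduction |
|---|---|---|
| 0.3 | 0.185 / 0.244 | 0.5% / 1.9% |
| 0.5 | 0.327 / 0.419 | 4.4% / 8.1% |
| 0.7 | 0.507 / 0.617 | 12.8% / 20.4% |

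Excluding current alcohol use disorder may restrict the AUDIT baseline in the same way. The criteria set no direct entry cut on PHQ-9, GAD-7 or PHQ-15.

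**The five-outcome model as planned.** This was simulated as seemingly unrelated regression by iterated maximum likelihood with sandwich standard errors. It used 22 + 23 analysed, 4,000 trials per cell, and between-measure correlation assumed at 0.3, 0.5 or 0.7. The SE ratio was 0.96–0.98, 0.86–0.87 and 0.71–0.73 for r = 0.3, 0.5 and 0.7, and 1.01–1.02 at r = 0. Coverage of the nominal 95% interval was 93–94% for both models in every cell.

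**Full retention.** With all 60 analysed, the arm-only half-width is 0.517 SD and the adjusted values are 0.498, 0.452 and 0.373 SD. The relative gains barely change.

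**The case against.** The strongest reply is that this is a feasibility pilot. None of the four research questions asks for a treatment effect, and progression turns on recruitment and on having 25-week ITQ data. The sample size carries no power claim, and r can be reported for sizing the full trial whichever model is fitted. All of this stands and limits the importance of the point. It does not remove it, because the plan itself names a primary between-arm analysis with p-values and effect sizes.

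The size of the gain is also assumed, and it is least certain for the ITQ, the named primary outcome. This stands. The range-restriction figures are illustrative too. The formula is for selection on the covariate itself, whereas entry uses a caseness rule on an earlier ITQ, and u has no source in the documents.

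A technical objection is partly right. The arm-only model is saturated. Own-baseline equations fix 20 cross-paths at zero (5 × 5 − 5), such as baseline PHQ-9 to 25-week ITQ. In simulations with strong correlation across measures and time, the ratio at r = 0.5 was 0.90–0.91 instead of about 0.86–0.87. A gain remained in every cell with r of 0.3 or more, without material bias.

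Finally, robust maximum likelihood with all available data does not answer the point: it cannot draw on baseline scores that the model omits.

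**Conclusion.** The point holds as a free improvement that should be made. The primary arm comparison is valid but less precise than the planned data allow. At 45 analysed, the expected reduction in standard error is about 3%, 12% or 28% for r = 0.3, 0.5 or 0.7. For the ITQ it may be only 0.5–2% at the low end. The possible loss is small: about 1%, and only if r is near zero.

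The reading of the plan is certain. The size rests on assumed values of r and u and on a linear relation between baseline and 25-week scores. Nothing about feasibility or progression changes.

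**What to change.** In Phase 2, regress each 25-week outcome on arm plus its own baseline score as a fixed covariate, within the same simultaneous model, and specify this before the outcome data are examined. Also:

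- Define the baseline as the pre-treatment measure in Recruitment, step 3. The eligibility score, "as indicated by the ITQ completed during their initial assessment", is a separate and earlier ITQ.
- If a baseline score is missing, fill it with the mean over all participants so that no observed 25-week outcome is dropped.
- Keep the arm-only model as a sensitivity analysis.
- Apply the same adjustment to the 12-week follow-up comparison, so that the two time points are analysed alike.
- State that baseline scores of the other measures are left out of each equation.
- Report r (pooled within arm) and the residual SD for each outcome, for sizing the full trial.

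The cost is SAP wording and minor programming, with no new data collection. The 25-week model grows from 25 parameters (5 intercepts, 5 arm effects, 15 residual variances and covariances) to 30, one slope per outcome.
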